9.1.4. Posttreatment Period (Follow-up)

All subjects will enter the 24-week Posttreatment Follow-up Period, except for subjects who withdraw consent. The latter subjects will be offered an optional safety Follow-up Visit, at which the assessments of the Week-4 Follow-up Visit need to be performed. During the Posttreatment Follow-up Period, site staff should enter the visit information via an IWRS at each scheduled visit (See the IWRS manual).

Any subject who withdraws consent during the Posttreatment Follow-up Period and/or notifies the site that he or she will not return for study visits, will be invited to do a Follow-up Visit at the time of withdrawal to complete the full set of protocol procedures as scheduled for the Week 24 Follow-up Visit. However, all possible efforts should be made to ensure that subjects complete the study.

Targeted physical examinations (ie, physical examinations directed at specific body systems as required based on the medical history and overall clinical presentation) (including body weight) and vital sign measurements will be performed at the Week-4 and Week-24 Follow-up Visits.

Echocardiogram and triplicate ECG will be performed at the Week-4 Follow-up Visit.

At the Week 12 Follow-up Visit, sparse PK sample will be taken at any time for the measurement of plasma concentrations of ODV.

Blood and urine samples for clinical laboratory assessments and urine pregnancy tests (for female subjects of childbearing potential) will be performed at the time points indicated in the TIME AND EVENTS SCHEDULE.

Blood sampling for determination of the HCV RNA level and for viral sequencing will be performed at all scheduled visits during follow-up. During follow-up, suspected relapse, ie, HCV RNA \geq LLOQ after previous <LLOQ, needs to be confirmed preferably within 2 weeks after the result has become available, and this retest may require an unscheduled visit, which should be scheduled by the investigator. At the time of the retest sample for HCV RNA, a sample for viral sequencing will also be collected.

All AEs, whether serious or nonserious, will be reported until the subject's last study visit. Pregnancies will be reported until the end of the study. The use of concomitant medication will be reported throughout the Posttreatment Follow-up Period.

9.2. Safety Evaluations

Any clinically relevant changes occurring during the study must be recorded in the Adverse Event Section of the eCRF.

All AEs, whether serious or nonserious, and pregnancies will be reported from the time a signed ICF is obtained until the subject's last study visit. The use of concomitant medication will be reported throughout the study period.

Any clinically significant abnormalities persisting at the end of the study or early withdrawal will be followed by the investigator until resolution or until a clinically stable endpoint is reached. The study will include the following evaluations of safety and tolerability according to the time points provided in the TIME AND EVENTS SCHEDULE:

9.2.1. Adverse Events

Adverse events will be reported by the subject (or, when appropriate, by a caregiver, surrogate, or the subject's legally acceptable representative) for the duration of the study. Adverse events will be followed by the investigator as specified in Section 12, Adverse Event Reporting.

9.2.2. Clinical Laboratory Tests

Blood samples for serum chemistry and hematology urine samples for urinalysis will be collected. The investigator must review the laboratory results, document this review, and record any clinically relevant changes occurring from signing of the ICF onwards until the subject's last study visit in the Adverse Event Section of the eCRF. The laboratory reports must be filed with the source documents.

Biochemistry samples on Day 1, Week 2, Week 4, EOT, Week 4 of follow-up, and Week 12 of follow-up must be taken after fasting for at least 8 hours. Lipid profile, insulin, and glucose are only to be assessed during visits with fasting samples.

The following tests will be performed by the central laboratory:

Hematology Panel

- hemoglobin - hematocrit	- white blood cell (WBC) count - WBC differential ^b :
- red blood cell (RBC) count ^a :	neutrophils
- RBC parameters:	lymphocytes
mean corpuscular hemoglobin	monocytes
mean corpuscular hemoglobin concentration	eosinophils
mean corpuscular volume	basophils
	- platelet count

^a An RBC evaluation may include abnormalities in the RBC count, RBC parameters, or RBC morphology, which will then be reported by the laboratory.

^b A WBC evaluation may include any abnormal cells, which will then be reported by the laboratory. In addition, any other abnormal cells in a blood smear will also be reported.

NCT02993250

Clinical Protocol 64294178HPC2003 Amendment 5

The samples will also be used for coagulation tests. Prothrombin time and activated partial thromboplastin time will be assessed at screening, Day 1, Week 4, Week 8 (cohort 2 only), EOT, follow-up Week 4, follow-up Week 12, and follow-up Week 24, and the International Normalized Ratio will be calculated. In addition, the hematology sample taken at screening will include testing for glycosylated hemoglobin.

• Se	erum Chemistry Panel	
- 5	sodium	- alpha-1 acid glycoprotein
- t	ootassium	- lipase
- (chloride	- CK
- (creatinine	- lactate dehydrogenase
- ł	olood urea nitrogen	- uric acid
- §	glucose ^a	- calcium (corrected for albumin)
- /	AST	- phosphate
- /	ALT	- serum albumin
- §	gamma-glutamyltransferase	- total protein
- t	otal, direct, indirect bilirubin	- total cholesterol
- i	nsulin ^a	- high-density lipoprotein cholesterol
- t	pancreatic amylase	- low-density lipoprotein cholesterol
- 8	alkaline phosphatase	- triglycerides
- t	hyroid stimulating hormone (TSH) ^b	- eGFR
	B-type natriuretic peptide (BNP) ^c	
a	$\begin{array}{c ccccccccccccccccccccccccccccccccccc$	

^a The homeostasis model assessment insulin resistance (HOMA-IR) index will be derived from plasma insulin and plasma glucose (fasting for at least 8 hours) test results performed on the biochemistry sample taken after fasting at baseline, EOT, and Week 12 follow-up.

- ^b TSH is to be assessed at screening and EOT or early withdrawal. In case TSH is not within the normal range, testing of fT3 and fT4 will be performed.
- ^c BNP is to be assessed at baseline, Week 2, Week 4, Week 6, EOT and Week 4 follow-up for cohort 1 and baseline, Week 2, Week 4, Week 6, Week 8, Week 10, EOT and Week 4 follow-up for cohort 2.

For each time point of the laboratory assessments, the selected central laboratory will also estimate the glomerular filtration rate.

• Urinalysis

Dipstick

- specific gravity
- pH
- glucose
- protein
- blood
- ketones
- bilirubin
- urobilinogen
- nitrite

- leukocyte esterase

Sediment (if dipstick result is abnormal)

- RBCs
- WBCs
- epithelial cells
- crystals
- casts
- bacteria

If dipstick result is abnormal, microscopy will be used to examine sediment. In the microscopic examination, observations other than the presence of WBCs, RBCs and casts may also be reported by the laboratory.

- Serum pregnancy testing will be performed at screening for women of childbearing potential. Urine pregnancy testing will be performed for women of childbearing potential only at the time points indicated in the TIME AND EVENTS SCHEDULE.
- Follicle-stimulating hormone will be tested at screening for female subjects who are postmenopausal for less than 2 years.
- Serology (HIV-1 and HIV-2 antibody, hepatitis A immunoglobulin M antibody, HBsAg, antiHBc, antiHBs, and hepatitis C antibody) will be performed at screening. Routine antibody testing will be performed to evaluate HIV infection status and additional testing will be done whenever clinically relevant.
- Hepatitis B virus DNA will be measured with PCR testing at the EOT Visit, or Treatment Withdrawal Visit, and may be evaluated at any time when there is a significant increase in the AST or ALT levels This only refers to subjects with antiHBc and/or antiHBs positive status at screening and not to subjects who have received HBV vaccine and are only antiHBs positive.
- An additional midstream urine sample must be provided at screening for a urine drug screening test. Drug screening involves analysis for amphetamines, benzodiazepines, cannabinoids, opioids and cocaine.
- In case of rash, safety blood samples (mandatory blood sample for safety in case of Grade 3 or 4 rash and at the discretion of the investigator in case of Grade 1 or 2 rash) might be taken at unscheduled visits as described in Section 9.2.8.1, and are to be processed by the local laboratory. The following parameters will need to be tested: AST, ALT, sedimentation rate, complete blood cell count (including hemoglobin, hematocrit, RBC count, WBC count, platelet count, neutrophils, lymphocytes, monocytes, eosinophils, and basophils), and creatinine.
- In the event a subject develops clinical signs suggestive of muscle injury (eg, proximal weakness, myalgias), a thorough workup (eg, assessment of CK, CK muscle-brain [CK-MB] fraction, aldolase, myoglobin, calcium, phosphate, creatinine, and urinalysis) for muscle injury should be performed by a central laboratory as described in Section 9.2.8.6.

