Hematology, biochemistry	X ^x	X ^{v,w,bb}			Х	X ^{v,bb}		$\underset{v,\text{bb}}{X}$	X^{bb}	X ^{bb}	X^{bb}	$X^{v,w,x,\text{bb}}$	X ^x	X ^{v,bb}	\mathbf{X}^{dd}	X ^{v,w}	\mathbf{X}^{dd}	Х
Urinalysis	X ^y	X			Х	Х		Х		Х		Х	Х	Х		Х		Х
HBV DNA ^{cc}												Х	Х					
Pharmacogenomics (blood sa	umple)																	
Host interleukin-28B (IL28B) genotyping		X																

Period	Screening Period ^a						T	reatn	nent P	eriod ^c						sttreati)w-up]		
Week/Day	W-6	Baseline ^b D1	D2	D3	W1	W2	W3	W4	W6	W8 ^{ff}	W10 ^{ff}	EOT (W8 or 12) ^{gg}	Treatment Withdrawal Visit ^d	W4 FU	W8 FU	W12 FU	W18 FU	W24 FU ^e
Study Procedures	•												•					
Ongoing Subject Review																		
Concomitant therapy	Х	Х	Х	Х	Х	Х	Х	Х	Х	Х	Х	Х	X	Х	X	Х	Х	Х
Adverse events ^z	Х	Х	Х	Х	Х	Х	Х	Х	Х	Х	Х	Х	Х	Х	Х	Х	Х	Х

Key: ALT=alanine aminotransferase; AST=aspartate aminotransferase; CT=computed tomography; BNP=B-type natriuretic peptide; D=day(s); DNA=deoxyribonucleic nucleic acid; ECG=electrocardiogram; EOT=end-of-treatment; ICF=informed consent form; LLOQ=lower limit of quantification; HBV=hepatitis B virus; antiHBc=hepatitis B core antibody; HCV=hepatitis C virus; FU: follow-up; MRI= magnetic resonance imaging; ODV=odalasvir; PK=pharmacokinetic; RNA=ribonucleic acid; SMV=simeprevir; TSH= thyroid stimulating hormone; W=week

- ^{a.} The first screening assessment has to be performed within 6 weeks prior to the Baseline Visit. Retesting of values (eg, safety laboratory or HCV RNA) that lead to exclusion will be allowed once during the Screening Period to assess eligibility. Any potential delays in the Screening Period will be discussed with the sponsor and evaluated on a case-by-case basis.
- ^{b.} All baseline assessments need to be performed before study drug intake.
- ^{c.} Subjects should ensure intake of study drugs up to 8 weeks (56 ± 1 days) or 12 weeks (84 ± 1 days) of treatment, in order to complete the indicated treatment duration. A Data Review Committee (DRC) will be established in this study to perform reviews with focus on the safety.

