- ^{m.} During follow-up, suspected relapse, ie, HCV RNA ≥LLOQ after previous <LLOQ, needs to be confirmed preferably within 2 weeks after the result has become available, and this retest may require an unscheduled visit which should be scheduled by the investigator.
- ^{n.} Viral sequencing will be performed at baseline by default in all subjects and at postbaseline in subjects not achieving sustained virologic response (SVR). Sequencing of additional samples may be triggered by the sponsor virologist.
- ^{o.} Sparse PK sampling for AL-335 (and metabolites), ODV, and SMV will be performed in all subjects.
- ^{p.} Sparse PK sample will be taken at predose, between 2 to 4-hours postdose, and between 4- to 6-hours postdose. Study drugs should be taken on site.
- ^{q.} Sparse PK sample will be taken any time during the visit for ODV only.
- ^{r.} No sparse PK sample will be taken for subjects participating in the rich serial PK substudy.
- ^{s.} Intake of study drugs should take place on site when predose PK sampling is performed.
- ^{t.} Complete physical examination (including height, body weight, and body systems) will be performed at screening (does not include breast, genitals, or rectal examination unless considered necessary by the investigator based on the subject's past and present medical history). At all other time points, a targeted physical examination based on the medical history and overall clinical presentation (including body weight) will be performed.
- ^{u.} Systolic and diastolic blood pressure and pulse rate need to be taken supine after at least 5 minutes of rest.
- ^{v.} Biochemistry samples must be taken after fasting for at least 8 hours at these visits as the lipid profile is also assessed.
- w. An additional blood sample for biochemistry should be taken for assessment of insulin and glucose after fasting for at least 8 hours.
- ^{x.} Thyroid stimulating hormone (TSH) is to be assessed at screening and EOT or early withdrawal.
- ^{y.} Includes a urine drug screening test.
- ^{z.} All adverse events (AEs), whether serious or nonserious, and pregnancies will be reported from the time a signed ICF is obtained until the subject's last study visit.
- ^{aa.} Subjects with cirrhosis have to receive an ultrasound scan, computed tomography (CT) scan, or magnetic resonance imaging (MRI) within 3 months prior to baseline/Day 1.
- ^{bb.} Includes assessment of B-type natriuretic peptide (BNP).

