- ^{cc.} HBV DNA will be evaluated at the EOT Visit, or Treatment Withdrawal Visit, and may be evaluated at any time when there is a significant increase in the AST or ALT levels. This only refers to subjects with antiHBc and/or HBs antibody [antiHBs] positive status at screening and not to subjects who have received HBV vaccine and are only antiHBs positive.
- ^{dd.} Serum chemistry panel only, excluding TSH, BNP, glucose, insulin, and low-density lipoprotein (LDL) and high-density lipoprotein (HDL) cholesterol.
- ee. Provision of study drug at Week 4 (all subjects) and 8 (Cohort 2 only) in principal.
- ^{ff.} Only for subjects enrolled in Cohort 2.
- ^{gg.} Week 8 (D56) for subjects enrolled in Cohort 1, and Week 12 (D84) for subjects enrolled in Cohort 2.

TIME AND EVENTS SCHEDULE: WEEK/DAY AND TIME WINDOWS

Period		Screening Period						Ті	eatmen	t Period	1						sttreatm ow-up P		
		W-6				W1 (D7)	W2 (D14)	W3 (D21)	W4 (D28)	W6 (D42)	-	-	EOT (D56)			W8 FU (D112)	W12 FU (D140)	W18 FU (D182)	W24 FU (D224)
Week/	Cohort 1	(D-42 to D0)	Baseline D1	D2	D3	-1 to + 1D (D6 to D8)	-2 to + 2D (D12 to D16)	-2 to + 2D (D19 to D23)	-2 to + 2D (D26 to D30)	-2 to + 2D (D40 to D44)		-	-1 to + 1D (D55 to D57)	Treatment Withdrawal Visit	-3 to + 3D (D81 to D87)	-7 to + 7D (D105 to D119)	-7 to + 7D (D133 to D147)	-7 to + 7D (D175 to D189)	-7 to + 7D (D217 to D231)
Day		W-6				W1 (D7)	W2 (D14)	W3 (D21)	W4 (D28)	W6 (D42)	W8 (D56)	W10 (D70)	EOT (D84)			W8 FU (D140)	W12 FU (D168)	W18 FU (D210)	W24 FU (D252)
	Cohort 2	(D-42 to D0)	Baseline D1	D2	D3	-1 to + 1D (D6 to D8)	-2 to + 2D (D12 to D16)	-2 to + 2D (D19 to D23)	-2 to + 2D (D26 to D30)	-2 to + 2D (D40 to D44)	-2 to + 2D (D54 to D58)	-2 to + 2D (D68 to D72)	-1 to + 1D (D83 to D85)	Treatment Withdrawal Visit	-3 to + 3D (D109 to D115)	-7 to + 7D (D133 to D147)	-7 to + 7D (D161 to D175)	-7 to + 7D (D203 to D217)	-7 to + 7D (D245 to D259)

TIME AND EVENTS SCHEDULE: RICH SERIAL PK ASSESSMENTS

Rich Serial PK Substudy^a (Approximately More Than 6 Subjects in Each Cohort^b)

Time of Visit	Sampling T	ìme	(hours)		·						
	Predose	ing	1 h	2 h	3 h	4 h	6 h	8 h	10 h	12 h	24 h
Week 4 ^c	X ^d	Dosi	Х	Х	Х	Х	Х	Х	Х	Х	X ^e

Key: h=hour(s); ODV=odalasvir; PK=pharmacokinetic; SMV=simeprevir

^{a.} This may require an overnight stay in the hospital.

^{b.} Rich PK sampling for AL-335 (and metabolites), ODV, and SMV will be performed in approximately more than 12 subjects (Cohorts 1 and 2 combined).

^{c.} Study drugs should be taken on site.

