11.4. Safety Analyses

The incidence of AEs will be summarized by body system and preferred term for each cohort and total. Changes from baseline in clinical laboratory values, vital signs, and ECG parameters

The safety analyses will be done separately for each study period (screening, treatment, and follow-up).

will be presented descriptively. The percentage of subjects with abnormal clinical laboratory,

Adverse Events

The verbatim terms used in the eCRF by investigators to identify AEs will be coded using the Medical Dictionary for Regulatory Activities (MedDRA). Treatment-emergent AEs are AEs with onset during the Treatment Period or that are a consequence of a preexisting condition that has worsened since baseline. All reported AEs will be included in the analysis. For each AE, the percentage of subjects who experience at least 1 occurrence of the given event will be summarized by treatment cohort. In addition, comparisons between treatment cohorts will be provided if appropriate.

Summaries, listings, datasets, or subject narratives may be provided, as appropriate, for those subjects who die, who discontinue treatment due to an AE, or who experience a severe or an SAE.

Clinical Laboratory Tests

Laboratory data will be summarized by type of laboratory test. Reference ranges and markedly abnormal results (specified in the SAP) will be used in the summary table of laboratory data. Descriptive statistics will be calculated for each laboratory analyte at baseline and for observed values and changes from baseline at each scheduled time point. A graphical presentation of changes in laboratory tests will be made as applicable.

Laboratory abnormalities will be assessed according to the WHO Toxicity Grading Scale (see Attachment 1) and the normal ranges of the clinical laboratory. Laboratory abnormalities will be tabulated by treatment cohort.

Electrocardiogram

The effects on cardiovascular variables will be evaluated by means of descriptive statistics and frequency tabulations. These tables will include observed values and changes from pretreatment values.

Electrocardiogram data will be summarized by ECG parameter. Descriptive statistics will be calculated at baseline and for observed values and changes from baseline at each scheduled time point. Frequency tabulations of the abnormalities will be made.

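### Footnote dd of the schedule leaves total cholesterol and triglycerides in the non-fasting follow-up Week 8 and Week 18 panel, although Section 9.2.2 limits the lipid profile to fasting visits

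*Protocol*

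**What the plan says.** Section 9.2.2 of the protocol sets the rule: "Lipid profile, insulin, and glucose are only to be assessed during visits with fasting samples". It names the fasting visits in the sentence before: "Biochemistry samples on Day 1, Week 2, Week 4, EOT, Week 4 of follow-up, and Week 12 of follow-up must be taken after fasting".

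The serum chemistry panel in the same section has four lipids: total cholesterol, HDL cholesterol, LDL cholesterol and triglycerides.

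In the Time and Events Schedule, the row "Hematology, biochemistry" marks the fasting visits with footnote v: "Biochemistry samples must be taken after fasting for at least 8 hours at these visits as the lipid profile is also assessed". Follow-up Weeks 8 and 18 carry footnote dd instead: "Serum chemistry panel only, excluding TSH, BNP, glucose, insulin, and low-density lipoprotein (LDL) and high-density lipoprotein (HDL) cholesterol".

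Section 11.4 plans the summary: "Descriptive statistics will be calculated for each laboratory analyte at baseline and for observed values and changes from baseline at each scheduled time point".

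**The concern.** Footnote dd is the more specific text for follow-up Weeks 8 and 18. It names what comes out of the panel, so someone setting up the central laboratory order could fairly conclude that any analyte not named stays in. Two of the four lipids are named and two are not. Because the footnote also removes glucose and insulin, it looks as though it was meant to carry out the fasting rule and missed two analytes. The protocol does not say which text prevails, and it does not itemise the lipid profile in a way that would leave these two out.

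The stake is small but real. Chemistry results belong to the safety data that form the primary endpoint (Section 2.1.2). The study is open-label and not randomised, and its cohorts differ by cirrhosis status, so no concurrent control would expose a sampling artefact. Section 1.2 also reports a Grade 3 cholesterol increase in one subject of the earlier Phase 2a study that evaluated these drugs, so lipid values may be looked at.

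**Working it through.** The protocol has no figure of its own to reproduce. The check compares the texts.

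**1. Panel at follow-up Weeks 8 and 18.** Take the Section 9.2.2 serum chemistry panel and remove what footnote dd excludes.

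| Analyte | In the Section 9.2.2 panel | Excluded by footnote dd | Left in at follow-up Weeks 8 and 18 |
|---|---|---|---|
| LDL cholesterol | yes | yes | no |
| HDL cholesterol | yes | yes | no |
| Glucose | yes | yes | no |
| Insulin | yes | yes | no |
| Total cholesterol | yes | no | **yes** |
| Triglycerides | yes | no | **yes** |

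**2. Fasting status.** The Section 9.2.2 list and footnote v agree: Day 1, Weeks 2 and 4, EOT, follow-up Weeks 4 and 12. Follow-up Weeks 8 and 18 are in neither. Steps 1 and 2 together give the conflict.

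**3. Other non-fasting biochemistry visits after baseline.**

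- Cohort 1 has 10 scheduled post-baseline biochemistry visits: Weeks 1, 2, 4 and 6, EOT, and follow-up Weeks 4, 8, 12, 18 and 24. Five are non-fasting: Weeks 1 and 6, and follow-up Weeks 8, 18 and 24.
- Cohort 2 adds Weeks 8 and 10, both non-fasting: 7 of 12.
- Only follow-up Weeks 8 and 18 carry an exclusion list. The remaining 5 − 2 = 3 visits in Cohort 1 and 7 − 2 = 5 in Cohort 2 rely on the Section 9.2.2 sentence alone. So does the Treatment Withdrawal Visit, when it takes place.

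**4. Possible effect on the summaries.** The documents give neither a food effect on these lipids nor a standard deviation, so no size can be derived from them. As an illustration under assumptions, let f be the share of subjects who have eaten and d the resulting shift, in standard deviations of the change. The shift in the mean change, divided by its standard error, is then f × d × √n.

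| Assumed d (f = 1) | n = 20 (√n = 4.47) | n = 40 (√n = 6.32) |
|---|---|---|
| 0.1 | 0.45 | 0.63 |
| 0.2 | 0.89 | 1.26 |
| 0.5 | 2.24 | 3.16 |

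If the Section 9.2.2 rule is followed there are no values to summarise. If subjects happen to attend fasting, f = 0 and the shift is zero. The plausible range therefore starts at nothing.

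**The case against.** The strongest reply is that Section 9.2.2 already settles the matter. Its rule is explicit and exclusive, and it must govern at Week 1, Week 6, Cohort 2 Weeks 8 and 10, the Treatment Withdrawal Visit and follow-up Week 24, where no footnote removes any lipid. If it governs there, it can govern at follow-up Weeks 8 and 18 too, and no non-fasting lipid is ever measured. In addition, the study tests no hypothesis (Section 2.2), lipids are not a named endpoint, and Section 11 leaves analysis details to an SAP that is not shown and could deal with non-fasting values.

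Much of this stands. A reader might infer that lipid changes at follow-up Weeks 8 and 18 are biased, with a rise, a fall at fasting Week 12, and another rise. The documents do not support that. It would require that footnote dd is followed over Section 9.2.2, that subjects have eaten, and that the analyte responds to food. A visit with no fasting requirement is not necessarily a visit after a meal. A reader might also count exactly two of the five follow-up visits as affected. That count lets Section 9.2.2 control follow-up Week 24 but not Weeks 8 and 18, so it says only where the texts conflict, not where values are distorted.

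The reply does not remove the conflict itself. At follow-up Weeks 8 and 18 a specific list competes with the general sentence. An SAP can decide how values are tabulated but not which analytes the laboratory is told to run.

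**Conclusion.** The protocol contradicts itself on total cholesterol and triglycerides at follow-up Weeks 8 and 18. This rests on wording alone and needs no assumption. The consequence is conditional: if those analytes are measured in subjects who have eaten, their change from the fasting Day 1 baseline is not comparable with the changes at the fasting visits. The documents do not show that this will happen, give no magnitude, and do not show that the two analytes would be affected alike. No error rate, power or efficacy result is touched. It is a minor inconsistency within descriptive safety laboratory data, worth correcting because it changes which values are collected and tabulated.

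**What to change.** - Add total cholesterol and triglycerides to the analytes excluded by footnote dd, so that it agrees with Section 9.2.2, and align the central laboratory order for follow-up Weeks 8 and 18.
- State in the schedule that lipids, glucose and insulin are run only at the fasting visits listed in Section 9.2.2. Correcting footnote dd alone would leave the remaining non-fasting biochemistry visits, including follow-up Week 24, dependent on a sentence elsewhere in the protocol.
- List any non-fasting lipid values already obtained, but leave them out of the change-from-baseline summaries. This can go in the SAP if it is not there already.

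The cost is one amended footnote, one added schedule note and a check of the laboratory set-up. At most, two total cholesterol and two triglyceride values per subject are given up at follow-up Weeks 8 and 18. No assessment that Section 9.2.2 permits is lost.
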